3. DESCRIPTION OF DESIGN AND TRIAL POPULATION

3.1 OVERALL TRIAL DESIGN AND PLAN

This is a randomised, double-blind, placebo-controlled, parallel-design dose-finding trial comprising of 4 active doses compared to placebo. Active treatment arms consist of active loading dose and active maintenance treatment. Two different loading doses and two different maintenance treatment doses are to be tested up to Week 16 (to give four different BI 655130 dose regimens). From Week 16 onwards, three different maintenance treatment doses are to be tested. The trial design is illustrated in [Figure 3.1: 1](#).

Approximately 140 eligible patients with Palmoplantar Pustulosis will be randomised in a 2:1:1:1:2 ratio to one of the 5 following treatment arms:

Arm 1: BI 655130	 (N=40)
Arm 2: BI 655130	 (N=20)
Arm 3: BI 655130	 (N=20)
Arm 4: BI 655130	 (N=20)
Arm 5: Placebo	 (N=40)

The randomisation will be stratified for Japan versus non-Japan and will be done to assure that sufficient patients per treatment arm are recruited specifically within each region (Japan vs non-Japan). Screening of patients into any single region (Japan or non-Japan) will be closed in order to ensure that not more than 91 patients are randomised into that region. The rationale is to allow for a thorough assessment in the Japanese population and to assess whether there is a difference in treatment effect between Japanese vs non-Japanese patients (which is hypothesized based on clinical trials in Japan which tend to show larger treatment effects in PPP patients than have been observed in European clinical trials). This stratum will be included into the analyses of the primary endpoint.

 This is required to keep the blinding. Please refer to [Sections 4.1.1](#) and [4.1.5.1](#) for details.

An overview of all relevant trial activities is provided in the [Flow Chart](#). For visit schedules and details of trial procedures at selected visits, refer to [Sections 6.1](#) and [6.2](#), respectively.

The patients are followed-up until Week 68 which is 16 weeks after the last dose of the study drug at week 52 (Residual Effect Period of 16 weeks).

[figure not shown]

Figure 3.1: 1 Trial design

An independent Data Monitoring Committee will evaluate safety and efficacy data on a continuous basis. For details please refer to [Section 8.7](#).

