6.2 DETAILS OF TRIAL PROCEDURES AT SELECTED VISITS

Study procedures to be performed at each visit are listed in the Flow Chart and respective protocol sections.

Measurement of vital signs should precede blood sampling and be assessed pre-dose at all dosing visits.

Patient Reported Outcomes (PROs) such as [REDACTED] Pain VAS, [REDACTED] [REDACTED] should be completed by the patient on his/her own in a pre-specified order in a quiet area/room before any other visit assessments or treatments, and, if possible, before any interaction with the investigator or other members of the study team. This applies also to the randomisation visit (V2).

The following sequence of procedures at each visit (where applicable) is recommended:

1. PROs (prespecified order: [REDACTED] Pain VAS, [REDACTED] [REDACTED])
2. AE and concomitant therapy collection; smoking status
3. Physical examinations (including predose vital signs)

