7.2.3 Secondary endpoint analyses

The following continuous secondary endpoints will be evaluated in the same manner as described for the primary endpoint:

- Change from baseline in PPP Pain VAS score at Week 4
- Change from baseline in PPP Pain VAS score at Week 16
- PPP SI change from baseline at Week 16

Hereby the same model shapes as for the primary endpoint will be used. The corresponding contrasts and further details will be described in the TSAP.

[figure not shown]
For the continuous secondary endpoint of percent change in PPP ASI from baseline at Week 52, the following maintenance treatment comparisons will be performed using an MMRM (incorporating weeks 4, 12, 20, 28, 36, 44, and 52) as well as descriptive methods:

- Arm 1 vs Arm 2: to compare the effect of [REDACTED] q4w vs [REDACTED] q4w on a loading dose of [REDACTED]
- Arm 3 vs Arm 4: to compare the effect of [REDACTED] q4w vs [REDACTED] q8w on a loading dose of [REDACTED]
- Arm 1 +Arm 3 +Arm 5 vs Arm 4: to compare the global effect of [REDACTED] q4w vs. [REDACTED] q8w maintenance dose used after Week 16.

- Arm 1 +Arm 3 +Arm 5 vs Arm 2: to compare the global effect of [REDACTED] q4w vs. [REDACTED] q4w maintenance dose.
- Arm 2 vs Arm 4: to compare the effect of [REDACTED] q4w vs. [REDACTED] q8w maintenance dose used after Week 16.

For each of the binary secondary endpoints at Week 16, a MCPMod approach will also be used to evaluate the treatment effect of multiple doses of BI 655130 vs. placebo. This method will be implemented for MCPMod in a binary setting. The assessments will be performed using the identical dose response assumptions to those described for the primary endpoint analysis and will be done based upon the response proportions collected at Week 16 only. The contrasts applicable to each dose response shape for each of the binary secondary endpoints, will be specified, along with further details on the implementation of a binary MCP-Mod approach, in the TSAP. [REDACTED]

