The primary analysis is planned to be performed once all patients have completed through the planned first 16 weeks of trial or early discontinued. The primary analysis will focus on individual patient's data up to treatment at week 16. If a patient early discontinued from treatment before week 16 or missed visit at week 16 but was still ongoing beyond week 16, all on-treatment data up to Day 127 which is the right limit of the week 16 extended time window (see [Table 6.7: 1](#)) will be included. In addition, for patients who missed visit at week

16 but was still ongoing beyond week 16, PPP Pain VAS, PPP ASI and PPP PGA assessments up to the first maintenance treatment after Week 16 (if available at time of primary analysis) will be included. They will not be reported in any outputs for primary analysis but might be used for imputation of endpoints related to PPP Pain VAS, PPP ASI and PPP PGA. See [Section 6.6.2](#) for the details of imputation methods.

The final trial analysis is planned to be performed at the end of the study once all randomized patients have completed the study (including any applicable follow-up period). The final trial analysis will include all trial data.

Treatment groups for the analysis of Arm 1-4 will be labelled and sorted as follows:

- **"Speso Low"**: (i.e., Arm 4)
- **"Speso Medium-low"**: (i.e., Arm 3)
- **"Speso Medium-high"**: (i.e., Arm 2)
- **"Speso High"**: (i.e., Arm 1)
- **"Speso Total"** (i.e., Arm 1, 2, 3 and 4), where appropriate for analysis up to Week 16

Treatment groups for Arm 5 will be labelled differently based on the data included in the analysis:

- **"Placebo & Speso"**: (i.e., Arm 5 if all trial data reported)
- **"Placebo"**: (i.e., Arm 5 if only data prior to the first Spesolimab treatment reported)
- **"Speso post placebo"**: (i.e., Arm 5 if only data post the first Spesolimab treatment reported)

If needed, Arm 1-5 could be pooled using the following label:

- **"Overall Total"**: (i.e., Arm 1, 2, 3, 4 and 5), where appropriate

For the analysis on safety data post Week 16, the following treatments will be added in addition to original treatments as follows (see [Section 7.8](#)):

- **"Speso [REDACTED]"** (i.e., Arm 1 + Arm 3 + Arm 5)

For the additional analysis on efficacy and safety data within loading stage, treatments will be re-grouped as follows (see [Section 7.6.4](#) and [Section 7.8](#)):

- **"Placebo"**: (i.e., Arm 5)
- **"Speso [REDACTED]"** (i.e., Arm 3 + Arm 4)

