For the primary analysis the dose-response relationship will be modeled using the total doses. Here, the total is the sum of all doses administered to the patient prior to the week 16 visit including both loading and maintenance phase. Thereby, it is assumed that the cumulative concentrations over time (AUC) and thus the cumulative total dose is the key driver of the efficacy response in the modelling part of MCPMod. [Table 7.4: 1](#) shows the calculated total doses per treatment arm.

Table 7.4: 1 Total dose per treatment arm.

High dose regime (Arm 1)	
Medium-high dose regime (Arm 2)	
Medium-low dose regime (Arm 3)	
Low dose regime (Arm 4)	
Placebo (Arm 5)	

W: Week.

The multiple comparison procedure will then be implemented using optimal contrast tests which control the family-wise type I error rate at a one-sided $\alpha = 0.05$. For the MCPMod test, the optimal contrasts of each candidate model are calculated using the R-function `optCont` using weights (w) proportional to the sample size of each dose group, respectively, and are shown in [Table 7.4: 2](#).

Table 7.4: 2 Contrast coefficient.

Model	Contrast coefficients for (total) dose				
	Placebo	Low dose: ██████████	Medium-low dose: ██████████	Medium-high dose: ██████████	High dose: ██████████
Linear	0.783	0.049	-0.049	-0.196	-0.587
Emax	0.869	-0.112	-0.151	-0.190	-0.416
Exponential	0.574	0.194	0.118	-0.106	-0.780
Logistic	0.706	0.220	-0.036	-0.279	-0.612
Sigmoid Emax	0.638	0.247	0.052	-0.256	-0.681

BI: Spesolimab total dose, ██████████ administered before week 16.

For the final evaluation, these contrasts will be updated using the expected model means from the candidate set and the estimated variance-covariance matrix extracted from the MMRM model. The updated contrast coefficients will be reported in the CTR.

Once the significance of a dose-response signal is established, the dose-response profile and the target dose can be estimated using a model averaging approach. Here, the final model is

derived as a weighted average over all significant model shapes. Here, the weights for each significant model (M_k) are given by

$$w(M_k) = \frac{\exp(0.5 \cdot AIC(M_k))}{\sum_{i=1}^K \exp(0.5 \cdot AIC(M_i))}$$

where $AIC(M_k)$ is the Akaike Information Criterion (AIC) of model M_k .

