Estimates for each dose group will be calculated and will be based on the final dose-response model. The choice of the target dose to be investigated in Phase 3 will be based upon efficacy as well as considering safety and other relevant information.

R code to perform the evaluations is available in [Section 9.4](#).

The following displays are planned.

- Table of the updated contrast coefficients per dose group and candidate model, together with the MCPMod test statistics and p-values for each model and the critical value
- For averaging model, figure of the dose-response curve
- For all significant model shapes, figures of the dose-response curve plus 95% confidence band (of the predicated shape) and 95% CI per dose (estimated from MMRM)
- For all significant model shapes, figure with the placebo corrected dose-response curve plus 95% confidence band (of the predicated shape).

R code is also available in [Section 9.4.1](#).

Descriptive statistics

Descriptive displays of percentage change from baseline in PPP ASI (with 95% CI) will be presented by treatment using OC and OC-IR methods respectively. The method to provide confidence intervals for each arm and unadjusted differences to placebo is derived from the Student's t-distribution.

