7.5.2 Secondary endpoints

Continuous secondary endpoints

Continuous secondary endpoints up to week 16 will be evaluated using MMRM model and MCP-Mod in the same way as for the primary endpoint.

For percent change in PPP ASI from baseline at Week 52, a similar setting to that described for the primary endpoint MMRM model (in [Section 7.4](#)) will be applied with the inclusion of the additional visits of Week 28, 40 and 52.

Binary secondary endpoints

For each of the binary secondary endpoints at Week 16, a logistic regression and MCPMod model will be used to evaluate the treatment effect of multiple doses of Spesolimab vs. placebo. This method will be implemented for MCPMod in a binary setting.

The primary analysis of binary secondary endpoints will be based on the FAS. Any data collected after use of any rescue therapy or after 6 weeks following last drug administration if a patient discontinued treatment early will be censored as the primary estimand (EC).

Logistic regression analysis

For binary endpoints, the difference in the proportion of patients with a response between Spesolimab and placebo will be analysed, for the FAS, using a logistic regression approach with a logit link via PROC LOGISTIC in SAS[®]. Fixed classification effects will include treatment and region (Japan vs. Non-Japan). In case 0 event is observed in any of the combination of dose group and strata a penalized regression based on the Firth's bias reduction method ([19](#), [20](#)) will be used.

The estimates from the logistic regression are on the logit scale, and the difference in proportions will be calculated as the difference between the predicted probabilities in the treatment groups on the original scale. Odds ratio will be also reported between each Spesolimab arm vs placebo

Confidence intervals will be calculated using the cumulative distribution function method of Reeve (14). More specifically, as suggested in Reeve (14), a numerical search algorithm will be employed to find the quantiles x_A of the cumulative distribution function, $F_{\widehat{\Delta p}}$, such that $F_{\widehat{\Delta p}}(x_A) = A$, where $A = 2.5\%$ and $A = 97.5\%$ and $F_{\widehat{\Delta p}}$ is given by equation (10) in Reeve (14). R code that will be used to implement this is provided in [Section 9.2](#).

MCP-MOD analysis

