
For AE, the additional safety tables for loading dose stage will be produced by re-grouping patients based on their loading doses [REDACTED] using SAF. The outputs

will include on-treatment data up to the first maintenance dose at week 8. If patient early discontinued from treatment prior to week 8 or missed treatment at week 8, then the safety data up to Day 71 (the right limit of the extended time window of week 8) will be included:

- Overview on TEAE
- TEAE by SOC, preferred term
- Serious TEAE
- All AESI
- UDAEC

AE over on-treatment period

In the final analysis, the additional selected tables for the overall period will be produced based on SAF to report AE occurring during whole treatment period from Day 1. Note that only Arm 1-4 will be reported:

- Overview on TEAE
- TEAE by SOC, preferred term
- Serious TEAE
- All AESI
- UDAEC

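### Week 4 PPP Pain VAS is modelled on dose totalled to Week 16, so arms treated identically at Week 4 are forced to different estimates

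*SAP*

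**What the plan says.** Protocol 7.2.3 lists change in PPP Pain VAS at Week 4 among the continuous secondary endpoints to be handled like the primary endpoint. It adds "Hereby the same model shapes as for the primary endpoint will be used" and leaves the contrasts and details to the SAP. The SAP's instruction is one sentence in 7.5.2: "Continuous secondary endpoints up to week 16 will be evaluated using MMRM model and MCP-Mod in the same way as for the primary endpoint". It makes no exception for Week 4 and shows no contrast table for continuous secondary endpoints.

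SAP 7.4 defines the dose axis for the primary analysis: "the total is the sum of all doses administered to the patient prior to the week 16 visit including both loading and maintenance phase". The stated rationale is that cumulative exposure, and hence cumulative dose, drives the response. After a significant test, "Estimates for each dose group will be calculated and will be based on the final dose-response model".

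The timing is set elsewhere:

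- Protocol 3.1: "Two different loading doses and two different maintenance treatment doses are to be tested up to Week 16".
- SAP 7.8, on the loading-stage safety tables: the outputs "will include on-treatment data up to the first maintenance dose at week 8".
- Protocol 6.2: patient-reported outcomes are completed "in a quiet area/room before any other visit assessments or treatments".
- SAP 6.1: "For the additional analysis on efficacy and safety data within loading stage, treatments will be re-grouped as follows". The groups that follow are placebo, Arms 3 + 4, and Arms 1 + 2.

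**The concern.** Doses planned for Week 8 onward cannot influence pain rated at Week 4. On the SAP's own rationale for the axis, the relevant dose at Week 4 is what has been given by then. That takes three values (placebo, lower loading, higher loading), not five.

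On the Week 16 axis, the two arms of each loading pair sit at different doses. Every candidate shape is strictly monotone, so a significant fit in the direction of benefit must rank Arm 1 above Arm 2 and Arm 3 above Arm 4, even if the observed arm means are equal or reversed. The Week 4 curve would then show an apparent maintenance-dose effect before any maintenance dose was given. Protocol 2.1.1 gives the secondary endpoints a supportive dose-ranging role, so this output could be read as dose information.

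**Working it through.** **1. Recover the dose axis.** The doses are blacked out, but the linear row of SAP Table 7.4: 2 determines their ratios. An optimal contrast is proportional to nᵢ(dᵢ − d̄), with n = 40/20/20/20/40 (Protocol 7.5). Hence

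relative dose = (c_placebo/n − cᵢ/nᵢ) / (c_placebo/n − c_high/n).

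The values c/n are 0.783/40 = 0.019575, 0.049/20 = 0.00245, −0.049/20 = −0.00245, −0.196/20 = −0.0098 and −0.587/40 = −0.014675. The denominator is 0.03425. The relative doses are 0 / 0.500 / 0.643 / 0.858 / 1, that is 0 : 7 : 9 : 12 : 14.

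**2. Reproduce the plan's own figures.** With d = (0, 7, 9, 12, 14), the weighted mean is 1120/140 = 8 and n(d − 8) = (−320, −20, 20, 80, 240), with norm √167200 = 408.9. Dividing gives −0.783, −0.049, 0.049, 0.196, 0.587. This is the printed linear row with the sign reversed. With the five shapes of Protocol 7.2.2, all 25 printed coefficients reproduce within 0.0005.

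**3. What separates the pairs.** Arm 1 − Arm 2 = 14 − 12 = 2 and Arm 3 − Arm 4 = 9 − 7 = 2. Arm 1 − Arm 3 = 5 and Arm 2 − Arm 4 = 5. This is the two-loading by two-maintenance structure. The within-pair step (2/14 = 0.14 of the top dose) is all maintenance, none of it given by Week 4.

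**4. Linear fit to error-free Week 4 means.** Set the true effects to (0, a, a, 1, 1), where a is the lower-loading effect as a fraction of the higher.

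- Sxx = 40·64 + 20·1 + 20·1 + 20·16 + 40·36 = 4360.
- Sxy = 20(−1)a + 20(1)a + 20·4 + 40·6 = 320. The terms in a cancel.
- Slope = 320/4360 = 0.0734, so the false gap within each pair is 2 × 0.0734 = 0.147, or 14.7% of the higher-loading effect for any a. (From the rounded printed contrasts it is 14.6% and 14.7%.)

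No Pain VAS effect is stated. Assumed effects of 10, 20 or 30 points give false gaps of 1.5, 2.9 or 4.4 points.

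**5. Averaged model.** Each case had 4,000 simulated trials. Significant shapes only were refitted and averaged with weights exp(−0.5·AIC). SAP 7.4 prints that exponent without the minus sign; the conventional sign is used here. Assumptions: effect 0.5 or 0.86 SD; a = 0.3, 0.5 or 0.9.

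| | Arm 1 vs 2 | Arm 3 vs 4 |
|---|---|---|
| Mean false gap, % of effect | 7–25 | 10–19 |
| SE of raw difference (SD units) | √(1/40 + 1/20) = 0.274 | √(1/20 + 1/20) = 0.316 |

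The gaps amount to about 0.2–0.6 of the raw SE. Between 99.6% and 100% of significant fits rank Arm 1 above Arm 2, and 100% rank Arm 3 above Arm 4.

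**6. The test itself.** Under a flat curve all contrasts have mean zero. The critical value is 1.923 and the simulated type I error is 5.0%. Efficiency is the squared ratio of a contrast's non-centrality to that of the optimal contrast. The best candidate keeps 0.957 at a = 0.3 (sigmoid Emax), 0.967 at a = 0.5 (linear) and 0.998 at a = 0.9 (Emax). Check for linear at a = 0.5: 320²/(4360 × 24.29) = 0.967. The lower/higher loading ratio is also blacked out. The recovered doses bound it at 7/12 = 0.58, since it equals (7 − x)/(12 − x) for a smaller maintenance total x ≥ 0. Over ratios 0.2–0.58 and effects 0.3–0.86 SD, power against a test on three loading levels differs by −2.4 to +1.6 percentage points.

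**The case against.** The strongest objection is that the specification is incomplete in the supplied text. SAP 7.4 ties the total-dose axis to the primary analysis, and the R code in 9.4 and the loading-stage efficacy analysis in 7.6.4 are not available. A Week 4 axis may exist there. That stands as a limit on certainty. It does not change what 7.5.2 says as written.

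Second, mitigation is already planned. The loading-stage analysis pools the same arms, and the primary displays put per-arm MMRM intervals beside each fitted curve, so two similar arm means would be visible. This is true, but the loading-stage analysis is additional, its endpoints are not visible, and neither item corrects the MCPMod curve or estimates.

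Third, the harm is modest. Ranking is forced by monotonicity, so the ranking percentages add little, and the gap size does respond to the data: at a = 0.9 and 0.86 SD, 24% of significant fits put Arms 1 and 2 within 2% of the effect. A separate simulation of the same six cases found the averaged-model estimate versus placebo closer to the truth than the unpooled arm estimate in every arm (root mean squared error 0.15–0.26 against 0.19–0.28 SD). This stands: modelling on the wrong axis can still beat not modelling. But pooling identically treated arms also reduces error without the bias. The SE against placebo is √(1/60 + 1/40) = 0.204 SD for Arms 1 + 2, compared with 0.224 SD for Arm 1 alone and 0.274 SD for Arm 2 alone.

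Finally, there is no key secondary endpoint, and no visible decision rule rests on Week 4 pain. That limits the importance of the point.

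**Conclusion.** The concern holds. As written, the Week 4 Pain VAS dose-response curve and the model-based per-arm estimates are biased, with a false within-pair difference of 14.7% of the higher-loading effect in a linear fit and about 7–25% in the averaged fit. The linear figure needs only the dose ratios recovered from Table 7.4: 2, the planned allocation, and equal true effects within each loading pair. The averaged figure also depends on the assumed effect sizes, the refit grid and the sign of the AIC weight.

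The test of a flat dose response, the MMRM arm means, the primary endpoint and the Week 16 endpoints are not harmed. This should be corrected, but it does not threaten the trial's main conclusion. Confidence is medium because SAP 7.6.4 and 9.4 could not be read.

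**What to change.** In SAP 7.5.2, give Week 4 Pain VAS its own dose axis: cumulative dose received before the Week 4 assessment, with levels placebo (n = 40), Arms 3 + 4 (n = 40) and Arms 1 + 2 (n = 60). Recompute the contrasts and keep only shapes that three levels can support. The four-parameter logistic and sigmoid Emax cannot be refitted, and Emax and exponential become saturated, so their fit cannot be checked. Alternatively, replace MCPMod at Week 4 with a comparison of the two pooled loading groups against placebo.

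Either choice departs from the protocol's commitment to the same shapes, so declare it in SAP Section 4. Keep the total-dose axis for the Week 16 endpoints. If 9.4 already uses a Week 4 axis, one sentence in 7.5.2 is enough.

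The cost is one SAP paragraph, one contrast table if MCPMod is kept, and one declared change. The downside is fewer candidate shapes and little or no gain in power (at most about 2.4 points). The benefit is that identically treated arms receive the same estimate.
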